## 5. STUDY DESIGN

This study is a Phase 1, investigator- and subject-blinded, randomized, placebo-controlled study in healthy Chinese subjects.

Subjects will be enrolled into 1 of 3 cohorts and receive single and multiple doses of lasmiditan or placebo in a parallel design. Each cohort will comprise 12 subjects (10 lasmiditan: 2 placebo) and will be assigned the following doses:

- Cohort 1 = 50 mg lasmiditan (or placebo)
- Cohort 2 = 100 mg lasmiditan (or placebo)
- Cohort 3 = 200 mg lasmiditan (or placebo)

Subjects will be evaluated for study eligibility  $\leq 28$  days prior to enrollment. Subjects who fulfil the eligibility criteria will be admitted to the clinical research unit (CRU) on Day -1 (the day before their first dose of lasmiditan or placebo).

After randomization on Day 1, investigational product (IP: lasmiditan or placebo) will be administered orally once on the morning of Day 1 after an overnight fast of at least 8 hours. Following a period of at least 72 hours without IP dosing, subjects will receive multiple once-daily oral doses of IP on Days 4 to 10 (7 days of dosing), after overnight fasts of at least 8 hours prior to each dose. The doses of lasmiditan administered on Days 4 to 10 will be the same dose as that administered on Day 1 for each subject.

Subjects will be discharged from the CRU on Day 12 following completion of all scheduled procedures and will attend a follow-up visit approximately 7 to 10 days following final oral dose of IP.

The planned study duration for each subject will be up to 50 days.

Blood samples will be collected for PK analysis. Safety and tolerability will be assessed throughout the study by means of adverse event (AE) review, physical examinations, vital sign measurements, 12-lead electrocardiograms (ECGs), clinical laboratory tests, and Columbia-Suicide Severity Rating Scale (C-SSRS).

## 6. TREATMENTS

The following is a list of the study treatment abbreviations that will be used in the TFLs.

Study Treatment Name	Treatment order in TFL
Placebo	1
50 mg lasmiditan	2
100 mg lasmiditan	3
200 mg lasmiditan	4

## 7. SAMPLE SIZE JUSTIFICATION

The sample size is customary for Phase 1 studies evaluating safety and PK, and is not powered on the basis of statistical hypothesis testing.

Subjects who are randomized but not administered treatment may be replaced to ensure that approximately 8 subjects per cohort, who receive lasmiditan, may complete the study.

## 8. DEFINITION OF ANALYSIS POPULATIONS

The “Safety” population will consist of all enrolled subjects who received at least 1 dose of IP, whether or not they completed all protocol requirements.

The “Pharmacokinetic” population will consist of all subjects who receive at least one dose of lasmiditan and have evaluable PK.

All protocol deviations that occur during the study will be considered for their severity/impact and will be taken into consideration when subjects are assigned to analysis populations.

Placebo subjects will be pooled across cohorts.

## 9. STATISTICAL METHODOLOGY

### 9.1 General

Data listings will be provided for all data that is databased. Summary statistics and statistical analysis will only be presented for data where detailed in this SAP. For continuous data, summary statistics will include the arithmetic mean, arithmetic standard deviation (SD), median, min, max and N; for log-normal data (e.g. the PK parameters: area under the concentration versus time curves [AUCs] and the maximum observed drug concentration [ $C_{max}$ ]) the geometric mean and geometric coefficient of variation (CV%) will also be presented. For categorical data, frequency count and percentages will be presented. Data listings will be provided for all subjects up to the point of withdrawal, with any subjects excluded from the relevant population highlighted. Summary statistics and statistical analyses will generally only be performed for subjects included in the relevant analysis population. For the calculation of summary statistics and statistical analysis, unrounded data will be used.

Mean change from baseline is the mean of all individual subjects' change from baseline values. Each individual change from baseline will be calculated by subtracting the individual subject's baseline value from the value at the timepoint. The individual subject's change from baseline values will be used to calculate the mean change from baseline using a SAS procedure such as Proc Univariate.

Data analysis will be performed using SAS® Version 9.4 or greater.

## 9.2 Demographics and Subject Disposition

Subject disposition will be listed. The demographic variables age, sex, race, ethnicity, country of enrolment, site ID, body weight, height and body mass index will be summarized and listed.

## 9.3 Pharmacokinetic Assessment

### 9.3.1 Pharmacokinetic Analysis

Pharmacokinetic (PK) parameter estimates will be determined using non-compartmental procedures in a validated software program (Phoenix WinNonlin Version 6.4 or later).

Plasma concentrations of lasmiditan (LY573144) and its metabolites (M7, M8, [S,R]-M18 and [S,S]-M18) will be used to determine the following PK parameters for single and multiple dose (unless otherwise specified), when possible:

Parameter	Units	Definition
$C_{\max}$	ng/mL	maximum observed drug concentration
$t_{\max}$	h	time of maximum observed drug concentration
$AUC_{\tau}$	ng.h/mL	area under the concentration versus time curve during one dosing interval (i.e. 24 h)
$AUC(0-t_{\text{last}})$	ng.h/mL	area under the concentration versus time curve from time zero to time $t$ , where $t$ is the last time point with a measurable concentration
$AUC(0-\infty)$	ng.h/mL	area under the concentration versus time curve from time zero to infinity (after single dose only)
$\%AUC(t_{\text{last}}-\infty)$	%	percentage of $AUC(0-\infty)$ extrapolated (after single dose only)
$t_{1/2}$	h	half-life associated with the terminal rate constant ( $\lambda_z$ ) in non-compartmental analysis
CL/F	L/h	apparent total body clearance of drug calculated after extra-vascular administration (LY573144 only)
$V_z/F$	L	apparent volume of distribution during the terminal phase after extra-vascular administration (LY573144 only)
$R_A$		accumulation ratio (based on $C_{\max}$ and $AUC_{\tau}$ ) (after multiple dose only - LY573144 only)
RI		linearity ratio between $AUC_{\tau}$ after multiple dosing day and $AUC(0-\infty)$ after single dosing day (LY573144 only)
MR		metabolic ratio a (after multiple dose only)

a no molar correction will be applied since the metabolites are very similar in molecular weight and within 5% of the molecular weight for lasmiditan.

Trough concentrations of lasmiditan and its metabolites will be evaluated graphically and descriptively for achievement of steady-state. No formal analysis will be performed for attainment of steady-state.

Additional PK parameters may be calculated, as appropriate. The software and version used for the final analyses will be specified in the clinical study report. Any exceptions or special handling of data will be clearly documented within the final study report.

Formatting of tables, figures and abbreviations will follow the Eli Lilly Global PK/PD/TS Tool: NON-COMPARTMENTAL PHARMACOKINETIC STYLE GUIDE. The version of the tool effective at the time of PK analysis will be followed.

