3.2. Background

Lasmiditan has a chemical structure and pharmacological profile that is distinct from triptans, which are the current standard of care for the treatment of acute migraine. It does not contain the indole group found in all triptans, but instead has a pyridinoyl-piperidine scaffold that is unique to antimigraine medications. Lasmiditan is a low-molecular-weight agonist of the 5-HT_{1F} receptor with a nonvascular and primarily neural mechanism of action. It has a high affinity for the human 5-HT_{1F} receptor and a >470-fold selectivity for the human 5-HT_{1F} receptor relative to the 5-HT_{1B} receptor.

Lasmiditan doses of 0.1 to 400 mg have been evaluated in healthy subjects or patients with migraine across completed Phase 1, 2, and 3 clinical studies. Cumulatively through 05 March 2018, a total of 3948 subjects/patients have received lasmiditan. The most frequently reported lasmiditan treatment-emergent adverse events (TEAEs) in the 2 Phase 3 placebo-controlled studies, in which patients treated 1 migraine attack with oral lasmiditan (50, 100, or 200 mg) or placebo, were dizziness, paresthesia, somnolence, fatigue, lethargy, and nausea, and the majority were mild or moderate in severity. Safety and tolerability in healthy subjects were similar up to the highest dose of 400 mg administered as a single and multiple (once daily for 7 days) dose, with tiredness, drowsiness, dizziness, and paresthesia being the most frequently reported adverse events (AEs). The majority of these were mild in severity, and none were severe.

Following dose administration of a single oral tablet to healthy subjects, lasmiditan was absorbed with a median t_{max} of 1.5 to 2.5 hours, and rapidly eliminated with a mean $t_{1/2}$ of approximately 4 hours. Over the clinical dose range of 50 to 200 mg, the mean estimates of lasmiditan C_{max} and $AUC(0-\infty)$ increased in a dose-dependent manner that was approximately linear with dose.

Following oral dosing with lasmiditan, up to 16 metabolites, including 3 major metabolites (M7, M8, and M18), were detected in human plasma and urine. These metabolites lacked significant pharmacological activity at the 5-HT_{1F} receptor and were generally considered to be pharmacologically inactive. The relative proportions of metabolites to intact lasmiditan

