remained reasonably constant throughout the oral dose range studied and their PK was approximately linear. The half-life of the metabolites ranged from approximately 4.5 to 21 hours.

The characterization of lasmiditan PK in Asian subjects has been limited. Therefore, it is not known whether there are PK differences between subjects of Asian descent, relative to the overall population.

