5.2. Number of Participants

Up to 36 subjects (12 subjects per cohort) may be enrolled and randomized so that approximately 8 subjects per cohort, who receive lasmiditan, complete the study. For purposes of this study, a subject completes the study when all scheduled procedures shown in the Schedule of Activities (Section 2) have been finished.

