10.3.2. Pharmacokinetic Analyses

10.3.2.1. Pharmacokinetic Parameter Estimation

Pharmacokinetic parameter estimates for lasmiditan and metabolites M7, M8, (S,R)-M18, and (S,S)-M18 will be calculated by standard noncompartmental methods of analysis.

The primary parameters for analysis will be area under the concentration versus time curve (AUC) from zero to infinity (AUC[0-∞]) [single-dose only], AUC over a dosing interval (AUC[0-τ]), maximum observed drug concentration (C_{max}), and time of maximum observed drug concentration (t_{max}). Other noncompartmental parameters, such as half-life, apparent clearance, apparent volume of distribution, and accumulation ratio may be reported.

Trough concentrations of lasmiditan and its metabolites will be evaluated graphically and/or descriptively for achievement of steady-state. No formal analysis will be performed for attainment of steady-state.

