### General PK Parameter Rules

- Actual sampling times will be used in the final analyses of individual PK parameters, except for non-bolus pre-dose sampling times which will be set to zero. For non-bolus, multiple dose profiles, the pre-dose time will be set to zero unless a time deviation falls outside of the protocol blood collection time window which is considered to impact PK parameter derivation.
- Both  $C_{max}$  and time of maximum observed drug concentration ( $t_{max}$ ) will be reported from observed values. If  $C_{max}$  occurs at more than one time point,  $t_{max}$  will be assigned to the first occurrence of  $C_{max}$ .
- AUC parameters will be calculated using a combination of the linear and logarithmic trapezoidal methods (linear-log trapezoidal rule). The linear trapezoidal method will be applied up to  $t_{max}$  and then the logarithmic trapezoidal method will be used after  $t_{max}$ . The minimum requirement for the calculation of AUC will be the inclusion of at least three consecutive plasma concentrations above the lower limit of quantification (LLOQ), with at least one of these concentrations following  $C_{max}$ . AUC(0- $\infty$ ) values where the percentage of the total area extrapolated is more than 20% will be flagged. Any AUC(0- $\infty$ ) value excluded from summary statistics will be noted in the footnote of the summary table.
- Half-life ( $t_{1/2}$ ) will be calculated, when appropriate, based on the apparent terminal log-linear portion of the concentration-time curve. The start of the terminal elimination phase for each subject will be defined by visual inspection and generally will be the first point at which there is no systematic deviation from the log-linear decline in plasma concentrations. Half-life will only be calculated when a reliable estimate for this parameter can be obtained comprising of at least 3 data points. If  $t_{1/2}$  is estimated over a time window of less than 2 half-lives, the values will be flagged in the data listings. Any  $t_{1/2}$  value excluded from summary statistics will be documented in the footnote of the summary table.
- A uniform weighting scheme will be used in the regression analysis of the terminal log-linear portion of the concentration-time curve.

- The parameters based on predicted  $C_{last}$  will be reported.

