### **9.3.2 Pharmacokinetic Statistical Methodology**

All PK parameters will be summarized by analyte and treatment, and listed. Plots of mean (+/- SD) plasma concentrations by analyte and treatment over time will be presented.

Pharmacokinetic parameters for lasmiditan will be evaluated to estimate dose proportionality over the 50 to 200-mg dose range on Day 1 and Day 10 separately and will be presented graphically, as well as in analysis tables. Log-transformed  $C_{max}$  and AUC parameters ( $AUC[0-\infty]$  for Day 1 and  $AUC\tau$  for Day 10) will be evaluated using a power model (where the log of the dose will be an explanatory variable) to estimate ratios of dose-normalized geometric means and the corresponding 90% confidence intervals (CIs). The estimated ratio between the highest and lowest doses will be used to assess dose proportionality. The intersubject coefficient of variation will be derived.

Example SAS code:

```
proc mixed data=pk01;  
  by param pkday;  
  title1 j=c "Estimate of slope";  
  model log_pk = log_dose / solution residual cl alpha=0.1;  
  estimate 'xx mg' intercept 1 log_dose yy / alpha=0.1 cl; /*Log value  
  of xx*/  
  estimate 'zz mg - xx mg' log_dose pp / alpha=0.1 cl; /*Difference in  
  log values of zz and xx*/  
  ods output estimates=estims;  
  ods output solutionf=doseprop;  
run;
```

Additional analysis will be performed if warranted upon review of the data.

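### Should the accumulation ratio be planned for the metabolites as well as for lasmiditan?

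*SAP*

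**What the plan says.** The parameter table in SAP 9.3.1 covers lasmiditan and four metabolites (M7, M8 and the two M18 isomers), after single and multiple dosing unless a row says otherwise. The rows for Cmax and AUCτ carry no analyte restriction. The R_A row, based on those two parameters, is marked "after multiple dose only - LY573144 only". CL/F, Vz/F and the linearity ratio RI are also limited to lasmiditan. No reason is given for the limit on R_A. The same section allows additional PK parameters and plans a descriptive look at troughs for the metabolites as well as the parent.

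SAP 9.3.2 states that "All PK parameters will be summarized by analyte and treatment, and listed". SAP 9.1 adds that "Summary statistics and statistical analysis will only be presented for data where detailed in this SAP".

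Protocol 10.3.2.1 leaves the ratio optional: "Other noncompartmental parameters, such as half-life, apparent clearance, apparent volume of distribution, and accumulation ratio may be reported". Metabolite PK is an exploratory objective, and Table LAIC.1 gives its endpoints as AUC(0-∞), Cmax and tmax. Protocol 3.2 describes the parent as "rapidly eliminated with a mean $t_{1/2}$ of approximately 4 hours" and says of the metabolites: "The half-life of the metabolites ranged from approximately 4.5 to 21 hours".

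**The concern.** A ratio that measures build-up under repeated dosing is planned for the analyte with the shortest half-life, where it should be close to 1. It is not planned for the analytes where it might approach two-fold. The reason that justifies the restriction for CL/F and Vz/F does not carry over. Those two need the fraction of dose converted to the metabolite, whereas R_A divides two observed exposures of the same analyte. The metabolic ratio does not fill the gap, because it is planned after multiple dosing only and so shows no change from Day 1.

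Under the general rule in SAP 9.1, a metabolite R_A would not be summarised by default. A reader who divided the Day 10 by the Day 1 geometric mean would get no between-subject CV%, and the two means might come from different subjects. At stake is how fully the exploratory metabolite objective describes repeated dosing.

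**Working it through.** The documents state no expected accumulation ratio, so there is no planned figure to reproduce.

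**Inputs from the documents.** τ = 24 h (SAP 9.3.1). Half-life is about 4 h for lasmiditan and about 4.5 to 21 h for the metabolites (Protocol 3.2). Doses are given on Day 1 and on Days 4 to 10 (Protocol 5.1). Median lasmiditan tmax is 1.5 to 2.5 h (Protocol 3.2).

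**Expected AUC accumulation.** With linear kinetics and half-life alone, R = 1/(1 − 2^(−24/t½)). If a metabolite forms from a parent with a 4-h half-life, R = AUC(0-∞)/AUC(0-24) for the sequential profile. The last column adds first-order absorption at an assumed 0.7 to 1.5 per h, which puts parent tmax at about 2.7 to 1.6 h.

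| Half-life | Half-life alone | Formation from parent | Formation plus absorption |
|---|---|---|---|
| 4 h (lasmiditan) | 1/(1 − 0.0156) = 1.016 | not applicable | 1.02 (absorption only) |
| 4.5 h | 1/(1 − 0.0248) = 1.025 | 1.11 | 1.12 to 1.14 |
| 21 h | 1/(1 − 0.4529) = 1.83 | 2.25 | 2.31 to 2.39 |

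For the actual schedule (seven daily doses plus what remains of the Day 1 dose), the half-life-alone value at 21 h is 1.82. The metabolite range is therefore about 1.03 to 1.8 on half-life alone, or about 1.1 to 2.4 with formation and absorption. A value of 2.4 from half-life alone would need a half-life of about 31 h.

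**What the planned outputs already show.** Cmax and AUCτ are derived for every metabolite on Day 1 and Day 10. On the log scale, the mean of the differences equals the difference of the means. If the same subjects contribute on both days, the ratio of the two geometric means is therefore exactly the geometric mean of the per-subject ratios. The CV% of those ratios can be calculated from the subject listings.

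**If the subjects differ.** Suppose 10 subjects supply Day 1 and a random 8 of them supply Day 10. The extra SD of the log ratio is σ·√(1/8 − 1/10) = 0.158σ. Between-subject CVs of 30% and 50% are assumed, since the documents give none:

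- CV 30%: σ = 0.294, extra error about 4.8%.
- CV 50%: σ = 0.472, extra error about 7.8%.

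At the larger value, a true 1.83 would read as about 1.70 to 1.97 (one SD: 1.83/1.078 and 1.83 × 1.078). That could not be mistaken for no accumulation.

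**The RI row.** Sampling ends at 48 h. At a 21-h half-life the share of AUC(0-∞) beyond 48 h is 2^(−48/21) = 20.5%, or 25.3% with formation from the parent. Both exceed the SAP's threshold, under which "values where the percentage of the total area extrapolated is more than 20% will be flagged". Keeping RI to lasmiditan is therefore reasonable.

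**The case for a change.** The strongest argument for a change is that it costs almost nothing: one table cell and a few output rows, with no new samples. It would put the ratio where it says most about repeated dosing. The SAP's allowance for additional parameters is a permission and does not commit the analysts. Troughs show whether steady state is reached, but not by how much AUC or Cmax has grown. All of this stands, and a team that chose to add the row would be doing something sensible.

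Other parts of the argument are weaker. The protocol mentions up to 16 metabolites and does not assign the 21-h half-life to any of the four being assayed, so near two-fold accumulation is possible but not established for them. The concern about unmatched subjects relies on a planning target that "approximately 8 subjects per cohort, who receive lasmiditan, complete the study", and completion there includes the follow-up visit. Day 10 AUCτ is fully observed by the 24-h sample on Day 11, while subjects are still resident in the unit. If all 10 reach that point with evaluable data, the extra error is zero. A metabolite at the short end of the range might fall below the assay limit by 24 h, but that is also where little accumulation is expected.

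**Conclusion.** No change to the plan follows. Limiting R_A to lasmiditan is a fair choice for an optional descriptive parameter. The metabolites are described as generally inactive, their PK is exploratory, and accumulation is not one of their listed endpoints. The SAP followed as written still gives Day 1 and Day 10 Cmax and AUCτ for each metabolite, in summary and by subject, together with troughs and half-lives. Accumulation can be read from these.

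What is given up is a ready-made summary of per-subject ratios. The central value would be unchanged if the same subjects supply both days. It would carry roughly 5% to 8% extra error (one SD) if two of ten were missing at random on Day 10, assuming between-subject CVs of 30% to 50%. The accumulation figures assume linear kinetics and the half-lives in Protocol 3.2, and the upper values also depend on the assumed formation and absorption rates. The conclusion is the same anywhere in those ranges, because no primary, secondary or stated exploratory result uses the ratio.

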### General PK Parameter Rules

- Actual sampling times will be used in the final analyses of individual PK parameters, except for non-bolus pre-dose sampling times which will be set to zero. For non-bolus, multiple dose profiles, the pre-dose time will be set to zero unless a time deviation falls outside of the protocol blood collection time window which is considered to impact PK parameter derivation.
- Both  $C_{max}$  and time of maximum observed drug concentration ( $t_{max}$ ) will be reported from observed values. If  $C_{max}$  occurs at more than one time point,  $t_{max}$  will be assigned to the first occurrence of  $C_{max}$ .
- AUC parameters will be calculated using a combination of the linear and logarithmic trapezoidal methods (linear-log trapezoidal rule). The linear trapezoidal method will be applied up to  $t_{max}$  and then the logarithmic trapezoidal method will be used after  $t_{max}$ . The minimum requirement for the calculation of AUC will be the inclusion of at least three consecutive plasma concentrations above the lower limit of quantification (LLOQ), with at least one of these concentrations following  $C_{max}$ . AUC(0- $\infty$ ) values where the percentage of the total area extrapolated is more than 20% will be flagged. Any AUC(0- $\infty$ ) value excluded from summary statistics will be noted in the footnote of the summary table.
- Half-life ( $t_{1/2}$ ) will be calculated, when appropriate, based on the apparent terminal log-linear portion of the concentration-time curve. The start of the terminal elimination phase for each subject will be defined by visual inspection and generally will be the first point at which there is no systematic deviation from the log-linear decline in plasma concentrations. Half-life will only be calculated when a reliable estimate for this parameter can be obtained comprising of at least 3 data points. If  $t_{1/2}$  is estimated over a time window of less than 2 half-lives, the values will be flagged in the data listings. Any  $t_{1/2}$  value excluded from summary statistics will be documented in the footnote of the summary table.
- A uniform weighting scheme will be used in the regression analysis of the terminal log-linear portion of the concentration-time curve.

- The parameters based on predicted  $C_{last}$  will be reported.

